3 SCHEDULE OF EVENTS

Study Procedure	Screening	Cycle 1				Cycle 2 - Cycle 6		End of Treatment	Follow-up	
Study Days	-14 to -1	1	2	8	15	1	15	Within 14 days of Treatment Discontinuation	30 and 90 Day Safety F/U	90 and 180 Day Disease Progression F/U Period
Visit Window	-	-	+1 day		±2 days	±2 days		±2 days	-2/+7 days	±30 days
Clinical Assessments										
Informed Consent	X									
Inclusion/exclusion criteria	X									
Demographics ¹	X									
Medical/Surgical/Cancer Histories ²	X									
Vital Signs ³	X	X	X	X	X	X	X	X	X	
Height	X									
Body Weight	X	X				X		X	X	
Physical Exam ⁴	X							X		
Symptom-directed Physical Exam		X	X	X	X	X	X		X	
ECOG Performance Status	X					X		X	X	
Concomitant Medications ⁵	X	X	X	X	X	X	X	X	X	
Adverse Events	X	X	X	X	X	X	X	X	X	X
Clinical Laboratory Assessments										
Full Blood Count ⁶	X	X	X	X	X	X	X	X	X	
Coagulation ⁶	X	X				X				
Serum Chemistry Panel ⁶	X	X	X	X	X	X	X	X	X	
Thyroid Function ¹²	X	X			X	X		X	X	
Urinalysis ⁶	X							X		
Pregnancy Test ¹⁰	X	X				X		X	X	
12-Lead Electrocardiogram	X							X	X	
HIV, Hepatitis B & C Tests ^{6,11}	X									
Study Drug Administration										

Study Procedure	Screening	Cycle 1				Cycle 2 - Cycle 6		End of Treatment	Follow-up	
Study Days	-14 to -1	1	2	8	15	1	15	Within 14 days of Treatment Discontinuation	30 and 90 Day Safety F/U	90 and 180 Day Disease Progression F/U Period
Visit Window	-	-	+1 day	±2 days		±2 days	±2 days	-2/+7 days	±30 days	
mRNA-2416 intratumoral injection ⁷		X			X	X	X ⁷			
Durvalumab infusion		X				X				
Tumor Assessments										
Tumor assessment ⁸	X					C3 & C5		X		X
PK/Pharmacodynamic Assessments										
PK Sampling ⁹		X	X	X		C2				
Cytokine Profile Sampling ⁹		X	X	X		C2				
Serum Immunogenicity Sample ⁹		X			X	X	C3 & C6	X		
Tumor Biopsy	X	Refer to Section 10.5								

1. Demographics include age, sex, race, and ethnicity.
2. Prior cancer history includes (i) date of diagnosis, (ii) staging, (iii) all previous therapies (ie, chemotherapy, immunotherapy, biologic or targeted agents, experimental therapies, radiotherapy, and surgery), (iv) previous therapy details (ie, regimen, start and stop dates), and (v) best response for each regimen.
3. Vital signs include temperature, blood pressure, preferably in seated position, and pulse rate. Pre-dose and as clinically indicated before every infusion or administration.

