4. Complete physical examination should include evaluation of the HEENT and neck and dermatologic, cardiovascular, respiratory, gastrointestinal (including assessments of liver and spleen), musculoskeletal, neurological, and lymphatic systems.
5. Please refer to Section 10.8 for additional detail regarding prior and concomitant medications
6. Please reference Appendix B Safety Laboratory Tests and Hepatitis Serology
7. Only for Arm A patients receiving treatment to superficial lesions. All patients in Arm B and patients in Arm A receiving treatment to visceral lesions are to receive intratumoral injections on Day 1 and Day 15 for Cycle 1, and on Day 1 only for Cycles 2-6. Please refer to Section 8.2 Study Design and Section 10.1 Intratumoral Injections for mRNA-2416 dosing requirements.
8. Please refer to Section 10.2 and 10.3 for tumor assessment imaging requirements
9. Please refer to Table 6 for PK, Cytokine Profile, and Serum Immunogenicity sampling details.
10. Females of child bearing potential only.
11. Testing for HIV and Hepatitis B or C is to be done locally. It is not required if a documented negative test within 6 months is available.
12. TSH and reflex free T3 or free T4g. If measured within 14 days prior to C1D1, it does not need to be repeated at C1D1.

TABLE OF CONTENTS

1	SPONSOR SIGNATURE PAGE	2
2	TABULATED PROTOCOL SUMMARY.....	12
3	SCHEDULE OF EVENTS.....	22
4	LIST OF ABBREVIATIONS	28
5	INVESTIGATORS AND STUDY ADMINISTRATIVE STRUCTURE	31
6	BACKGROUND AND RATIONALE.....	32
6.1	INDICATION BACKGROUND	33
6.2	MRNA-2416 BACKGROUND	33
6.3	DURVALUMAB BACKGROUND.....	35
6.4	MRNA-2416 DOSING RATIONALE	36
6.5	DURVALUMAB DOSING RATIONALE.....	37
6.6	PATIENT POPULATION	38
6.7	STATEMENT OF COMPLIANCE.....	38
7	STUDY OBJECTIVES AND ENDPOINTS.....	39
7.1	PRIMARY OBJECTIVES.....	39
7.2	PRIMARY ENDPOINTS	39
7.3	SECONDARY OBJECTIVES.....	39
7.4	SECONDARY ENDPOINTS.....	40
7.5	EXPLORATORY OBJECTIVES.....	40
7.6	EXPLORATORY ENDPOINTS	40
7.7	SAFETY PARAMETERS.....	41
8	STUDY DESIGN	42
8.1	NUMBER OF PATIENTS	42
8.2	STUDY DESIGN	42
8.2.1	ARM A DOSE ESCALATION PERIOD	43
8.2.2	ARM A DOSE ESCALATION BIOPSY COHORT ENRICHMENT	44
8.2.3	ARM B DOSE ESCALATION PERIOD	44
8.2.4	DOSE CONFIRMATION IN VISCELAR LESIONS.....	45
8.2.5	ARM A PHASE II DOSE EXPANSION PERIOD	45
8.2.6	ARM B PHASE II DOSE EXPANSION PERIOD.....	45
8.2.7	PHASE II DOSE EXPANSION PERIOD STOPPING RULES	45
8.3	STUDY FLOW AND EXPECTED DURATION OF PATIENT PARTICIPATION.....	46

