8.3 STUDY FLOW AND EXPECTED DURATION OF PATIENT PARTICIPATION

All patients will participate in a Screening Phase, Treatment Phase, and Follow-up Phase.

Screening Phase:

- A 14-day screening period before enrollment (\leq 28 days for baseline biopsy and imaging)
- Patients will be evaluated against study inclusion and exclusion criteria. Patients must meet all inclusion criteria and none of the exclusion criteria at screening in order to be eligible for the study. Assessments required on C1D1 that are performed as part of the screening evaluations and within 72 hours prior to the first dose of study treatment, do not need to be repeated on C1D1.

Treatment Phase:

- Arm A: mRNA-2416 administered for 6 cycles
- Arm B: Combination dosing of mRNA-2416 with durvalumab for 6 cycles. Following completion of 6 cycles of combination dosing, patients may continue with durvalumab as a single-agent until disease progression, unacceptable toxicity, or 24 months of treatment (total), whichever is sooner.

Safety Follow-up:

- Patients will be followed up for safety evaluation 30 and 90 days after their last dose of study treatment.

Disease Progression Follow-up:

Patients who complete study treatment with an overall tumor assessment of stable disease (SD) or better will be followed for tumor assessment 60 and 180 days after their last dose of study treatment, or until disease progression, whichever occurs first.

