Grade 3 or 4 (Grade 3 diarrhea: stool frequency of ≥ 7 over baseline per day; Grade 4 diarrhea: life threatening consequences) (Grade 3 colitis: severe abdominal pain, change in bowel habits, medical intervention indicated,	Grade Permanently discontinue study drug/study regimen for Grade 3 if toxicity does not improve to Grade ≤ 1 within 14 days; study drug/study regimen can be resumed after completion of steroid taper.	3	For Grade 3 or 4: 
– Promptly initiate empiric IV methylprednisolone 2 to 4 mg/kg/day or equivalent.– Monitor stool frequency and volume and maintain hydration.– Urgent GI consult and imaging and/or colonoscopy as appropriate.– If still no improvement within 3 to 5 days of IV methylprednisolone 2 to 4 mg/kg/day or equivalent, promptly start further immunosuppressives (eg, infliximab at 5 mg/kg once every 2 weeks). Caution:

Specific immune-mediated reactions

Adverse Events	Severity grade of the Event (NCI CTCAE version 4.03)	Dose modifications	Toxicity management
	peritoneal signs; Grade 4 colitis: life-threatening consequences, urgent intervention indicated)	Grade 4 Permanently discontinue study drug/study regimen.	
Ensure GI consult to rule out bowel perforation and refer to infliximab label for general guidance before using infliximab.
 
Once the patient is improving, gradually taper steroids over ≥ 28 days and consider prophylactic antibiotics, antifungals, and anti-PJP treatment (refer to current NCCN guidelines for treatment of cancer-related infections [Category 2B recommendation]).^a
Hepatitis (elevated LFTs)	Any grade	General guidance	For any grade: 
Monitor and evaluate liver function test: AST, ALT, ALP, and TB.Evaluate for alternative etiologies (eg, viral hepatitis, disease progression, concomitant medications).
	Grade 1 (AST or ALT $> \text{ULN}$ and $\leq 3.0 \times \text{ULN}$ and/or TB $> \text{ULN}$ and $\leq 1.5 \times \text{ULN}$)	
No dose modifications.If it worsens, then treat as Grade 2 event.	For Grade 1: 
Continue LFT monitoring per protocol.

Specific immune-mediated reactions

Adverse Events	Severity grade of the Event (NCI CTCAE version 4.03)	Dose modifications	Toxicity management

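### Arm B patients may take single-agent durvalumab up to 24 months, but no blood count, chemistry, thyroid or pregnancy test, ECOG or symptom-directed exam is scheduled after Cycle 6

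*Protocol*

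**What the plan says.** Under the Treatment Phase in Protocol Section 8.3, Arm B patients who finish six cycles of the combination "patients may continue with durvalumab as a single-agent until disease progression, unacceptable toxicity, or 24 months of treatment (total". SAP Section 3.1 repeats this. SAP Section 7.3 counts the single-agent period in durvalumab exposure, and SAP Section 5.1 has a disposition category for finishing two years of durvalumab. The dose is given every four weeks (Protocol Section 6.5).

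The last on-treatment heading in the Schedule of Events (Protocol Section 3) is "Cycle 2 - Cycle 6", and the next column is End of Treatment. Even the row "Durvalumab infusion" has no entry beyond Cycle 6.

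Some assessments carry on under other text:
- vital signs before each infusion, and weight at each visit (Section 10.2; footnote 3 of the schedule for vital signs);
- tumor assessment every 56 days (Section 10.10);
- adverse event collection (Section 12.2);
- concomitant medication reporting (Section 10.8).

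In the Appendix E hepatitis guidance, the any-grade row says "Monitor and evaluate liver function test: AST, ALT, ALP, and TB" and the Grade 1 row says "Continue LFT monitoring per protocol". The nephritis rows for Grades 1 and 2 likewise send the reader back to creatinine monitoring under the protocol. SAP Section 9.2 takes laboratory timing from the protocol and adds no visits.

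**The concern.** Durvalumab's listed risks include hepatitis, nephritis, pancreatitis and endocrinopathy (Sections 6.3 and 12.1.5). For the liver and kidney, Appendix E acts on laboratory multiples. AST or ALT above 3 x ULN means hold; creatinine above 3 x baseline means permanent discontinuation. It also requires a hold for Grade 3 or higher amylase or lipase elevations without symptoms, and both enzymes belong to the chemistry panel in Appendix B.

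Early rises in these values can be silent, so vital signs, scans and adverse event questioning do not replace the tests. If no test is required, a site can follow the protocol exactly and never obtain the value that would stop dosing. The analysis is affected too: SAP Sections 9.2.1 and 9.2.2 tabulate worst post-baseline values and grade shifts. Single-agent exposure would be counted while laboratory toxicity during it may go unrecorded, or be recorded unevenly across sites.

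Thyroid results matter less for dosing. Endocrine holds turn on clinical stability or symptom control and exempt hypothyroidism, but the work-up still assumes measurements repeated over cycles.

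**Working it through.** **Step 1. What is scheduled.** The counts come from the Schedule of Events. Cycle 1 has Days 1, 2, 8 and 15; Cycles 2-6 have Days 1 and 15. Ranges arise for three reasons:
- Arm B has no injection on Day 15 of Cycles 2-6 (footnote 7), so that visit may not be attended.
- Section 8.3 lets Cycle 1 Day 1 assessments be skipped: those done "within 72 hours prior to the first dose of study treatment, do not need to be repeated on C1D1".
- Footnote 12 does the same for thyroid function: "If measured within 14 days prior to C1D1, it does not need to be repeated at C1D1".

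| Assessment | Cycles 1-6 | Cycle 7 to End of Treatment |
|---|---|---|
| Blood count | 4 + 2 x 5 = 14; 4 + 5 = 9 without Day 15 of Cycles 2-6; 8 if C1D1 is also waived | 0 |
| Chemistry, including liver tests and creatinine | same as blood count: 8 to 14 | 0 |
| Thyroid function | 2 + 5 = 7; 6 with the waiver | 0 |
| Pregnancy test ("Females of child bearing potential only") | 1 + 5 = 6; 5 with the waiver | 0 |
| ECOG | 5 | 0 |
| Symptom-directed exam | 4 + 10 = 14; 9 without Day 15 of Cycles 2-6 | 0 |

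None of the 12 footnotes extends these rows.

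**Step 2. Whether Appendix E fills the gap.** Its any-grade rows name the tests but give no interval for a patient without an event. Its low-grade rows point back to protocol monitoring. After Cycle 6 that reference leads to a schedule with no entry.

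**Step 3. Length of the gap for a patient treated to the limit.** Six cycles last 6 x 28 = 168 days. The documents do not define 24 months in days, so both readings are shown.
- Calendar months, at the 30.4375 days per month used in SAP Section 6.2: 24 x 30.4375 = 730.5 days. 730.5 - 168 = 562.5 days, which is 562.5/30.4375 = 18.5 months, 562.5/730.5 = 77.0% of treatment, and 562.5/28 = 20.1 cycles.
- Four-week cycles: 24 x 28 = 672 days. 672 - 168 = 504 days, which is 16.6 months, 75.0% of treatment, and 18 cycles.

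**Step 4. Shorter treatment.** The stop times are assumed, on calendar months.
- 12 months: 365.25 - 168 = 197.25 days (54.0%, 7.0 cycles).
- 9 months: 273.9 - 168 = 105.9 days (38.7%, 3.8 cycles).

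**The case against.** The best counter-arguments concern size and intent, because no passage schedules the missing tests.

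- **The figure is a ceiling.** Continuation is optional and ends at progression. Expansion patients are platinum resistant or refractory with at least two prior lines, and Section 6.1 cites response rates of 11% to 17% for PD-1/PD-L1 inhibition in recurrent ovarian cancer. Few may reach 24 months. This stands: the size is per patient, and the number affected is unknown.
- **The calendar reading is the likelier one.** SAP Section 5.1 speaks of two years. This also stands; it favors the larger figure, and 504 days is only a lower bound.
- **Day 168 is not the last test.** The last tabulated test is Cycle 6 Day 15 (5 x 28 + 15 = Day 155), or Cycle 6 Day 1 (Day 141) if Day 15 is not attended. On calendar months the time since the last test is then 730.5 - 155 = 575.5 or 730.5 - 141 = 589.5 days. Counting from Day 168 therefore understates it.
- **End of Treatment might fall after Cycle 6.** Section 10.5 lists completing six cycles with stable disease or better as a reason to discontinue study therapy, and SAP Section 5.1 treats six durvalumab cycles as completion. On that reading the End of Treatment, 30-day and 90-day visits supply some tests, but only to about 168 + 90 + 7 = Day 265. For a patient reaching 24 months, 730.5 - 265 = 465.5 days (or 672 - 265 = 407) would still have none, and the safety visits would already be used. Section 8.3 itself places continued durvalumab inside the Treatment Phase.
- **Testing was probably intended.** Sections 7.7 and 12 list laboratory tests among the safety measures without a cycle limit, and sites may test as routine care. The table was plausibly just not updated when the continuation was added. That may explain the gap, but those sections set no interval and require no test at any visit. The case report form was not available, so actual collection cannot be judged.

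**Conclusion.** The concern holds. As written, the protocol permits single-agent durvalumab after Cycle 6 and schedules none of the six listed assessments between then and End of Treatment. The laboratory-driven liver and kidney rules therefore have no required routine input during that period.

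For a patient treated to the limit, this covers about three quarters of total treatment time. That ceiling assumes End of Treatment follows the last durvalumab dose. It shrinks quickly with earlier stopping, and the documents do not say how many patients continue.

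This is a safety-monitoring gap that should be closed. It lies outside the 28-day DLT window and does not affect the response-rate endpoint, the sample size or the error rates.

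**What to change.** Add a durvalumab-only column to the Schedule of Events: Cycle 7 onward, Day 1, every four weeks. Carry forward the Day 1 safety rows from Cycles 2-6: blood count, chemistry with liver tests, thyroid function, pregnancy test where applicable, ECOG, symptom-directed exam, weight, vital signs, adverse events and concomitant medications. Show the durvalumab infusion there, and the 56-day scans that Section 10.10 already requires.

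The cost is a protocol amendment to one table, plus routine blood draws and data entry at infusion visits patients already attend. That is at most about 18 to 20 extra Day 1 draws for a patient who reaches 24 months.

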8.4 DOSE ESCALATION PROCEDURES

8.4.1 SAFETY REVIEW COMMITTEE (SRC)

A SRC composed of the study Medical Monitor, Sponsor representatives, and enrolling Principal Investigators (PIs) will hold teleconferences at the completion of each dose cohort in the Dose Escalation Period and during the Expansion Period, as needed, to review and assess all available safety data and the treatment status of all patients.

A written summary documenting the results, and recommendations of each review, including SRC consensus regarding recommended dose escalations or MTD/RDE, will be provided to the investigator(s) and maintained on file with the Sponsor. Additional personnel may participate in reviews as indicated.

Following a cohort review, the mRNA-2416 SRC may recommend proceeding with enrollment in the next dose cohort, enrolling additional patients in the current cohort, dropping back to a lower cohort, or not enrolling any additional patients. The dose escalation guidelines outlined in [Section 8.4.4](#), as well as the study stopping rules outlined in [Section 8.2.6](#), will be used as the basis for all SRC decisions.

While the SRC is expected to reach a consensus opinion regarding any premature discontinuation or significant modification of the study, the Sponsor may independently stop the study.

8.4.2 DEFINITION OF DOSE-LIMITING TOXICITIES

A dose-limiting toxicity (DLT) is defined as an adverse event or abnormal laboratory value assessed as unrelated to disease, disease progression, inter-current illness, or concomitant medications and at least possibly related to the study therapy and that occurs within the first 28 days of study therapy. The investigator must notify the Sponsor immediately of any DLTs.

For patients in Arm A receiving mRNA-2416, the following toxicities will be considered a DLT:

- All Grade 3 AEs with the exception of the following:
 - Grade 3 thrombocytopenia lasting <7 days
 - Grade 3 neutropenia without fever or lasting <7 days
- Any Grade 4 or Grade 5 toxicity. Death due to disease progression is not considered a DLT.

For patients in Arm B receiving mRNA-2416 in combination with durvalumab, the following toxicities will be considered a DLT:

Adverse Event (AE)+C2:F16	DLT Criteria		
	Grade 2 Events	Grade 3 Events	Grade 4 events
Diarrhea/colitis	none	Events that do not resolve to Grade 1 or baseline within 14 d (whether or not it is immune-mediated)	DLT
Pneumonitis	Non-infectious pneumonitis that does not resolve to Grade ≤1 within 10 days	Non-infectious pneumonitis is a DLT	DLT
Hepatitis	none	Alanine aminotransferase (ALT) or aspartate aminotransferase (AST) >8×ULN or total bilirubin (TBL) >5×ULN OR events meeting Hy's Law (AST or ALT ≥3×ULN with concurrent increase in TBL ≥2×ULN without evidence of cholestasis or alternative explanations)	DLT
Rash	Any grade rash with bullous formation.	Rash not resolving to Grade 1 or baseline within 30d. Any rash with bullous formation.	DLT
Peripheral neuromotor syndromes such as Guillain-Barre or myasthenia gravis	Events not resolving to Grade 1 within 30d. Events with any signs of respiratory insufficiency or autonomic instability.	Events that do not resolve to Grade 1 within 30d. Events with any signs of respiratory insufficiency or autonomic instability.	DLT
Myocarditis	Events that do not resolve to Grade 1 within 3d OR a biopsy confirms immune-mediated myocarditis.	All Grade 3 myocarditis.	DLT
Myositis/polymyositis	Events that do not resolve to Grade 1 within 30d OR exhibit signs of respiratory insufficiency regardless of optimal medical management	Events that do not resolve to Grade 1 within 30d OR exhibit signs of respiratory insufficiency regardless of optimal medical management	DLT
Endocrinopathies involving thyroid or pituitary glands or adrenal insufficiency	none	Excludes events that are managed with or without systemic corticosteroid therapy and/or hormone replacement therapy and the patient is asymptomatic	
Type I diabetes mellitus	none	Events that are not managed with appropriate diabetic therapy	
Nephritis	none	Any immune-mediated increase in creatinine >3×ULN, or >3×baseline for patients with a baseline creatinine elevated above ULN	DLT
Elevated amylase or lipase/pancreatitis	none	Elevations in amylase or lipase >2.0×ULN with signs or symptoms of pancreatic inflammation	
All other imAEs OR non-imAEs	none	Events that do not resolve to Grade 1 or baseline within 30d	DLT
Infusion-related reactions	none	Events that do not resolve within 6h despite appropriate medical management.	DLT

- Any Grade ≥ 3 immune or non-immune adverse event (AE) that is at least possibly related to the investigational product (IP) or investigational regimen (IR) with two exceptions: Any grade of vitiligo or alopecia
- Hematologic toxicity:
 - Grade ≥ 3 neutropenia complicated by fever $>38.3^{\circ}\text{C}$
 - Grade 4 neutropenia (lasting more than 7 days)
 - Grade ≥ 3 thrombocytopenia with significant bleeding
 - Grade 4 thrombocytopenia (regardless of duration)
 - Grade 4 anemia (regardless of duration)

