8.4.3 DEFINITION OF MTD

The MTDs will be defined as the highest dose of mRNA-2416 alone and in combination with durvalumab at which a DLT has been seen in less than 2 of 6 patients (<33%) during the first 28-days of study therapy.

If 2 or more adverse events that meet the definition of a DLT as defined in [Section 8.4.2](#), are observed beyond the first 28 days of study therapy within a dose escalation cohort, further enrollment may be held, pending safety analysis of the events by the SRC. These events will not affect the determination of the MTD but will be used in determining the appropriate RDE.

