8.4.4 DOSE ESCALATION PROCEDURE

In order to be evaluable for dose determination, a patient must have received $\geq 50\%$ of the planned mRNA-2416 dose and $\geq 75\%$ of the planned durvalumab dose (Arm B) for Cycle 1 and must either have been followed ≥ 28 days following the first dose or have experienced a DLT within 28 days of the first dose. Patients who are not evaluable for dose determination may be replaced.

Dose escalation determination will not occur until the third patient in a cohort has completed their first 28-day study therapy.

- If no patient (0 of 3) in a dose cohort experiences a DLT during the first 28 days, then the next dose cohort of 3 patients will be enrolled at the next dose level per [Table 1](#) following consensus of the SRC.
- If 1 of 3 patients in a dose cohort experiences a DLT, an additional 3 patients will be enrolled in that dose cohort.
 - Provided that no more than 1 of 6 patients in the expanded dose cohort experiences a DLT within 28 days of the first dose, then a dose cohort of 3 patients will be enrolled at the next dose level per [Table 1](#) following consensus of the SRC.
- If ≥ 2 patients in a dose cohort experience a DLT within 28 days of the first dose, that cohort will have exceeded the MTD. No additional patients will be dosed at that level, and 3 patients will be enrolled in the preceding dose cohort, unless 6 patients have already been treated at that dose level. Using the same criteria, lower dose cohorts will be explored as the MTD until ≤ 1 of 6 patients experiences a DLT.

In the event that ≥ 2 of the first 6 DLT-evaluable patients in the 1.0 mg cohort experience a DLT, then the next cohort will be dosed with 0.5 mg mRNA-2416.

In the event that ≥ 2 of the first 6 DLT-evaluable patients in the 8.0 mg cohort experience a DLT, an intermediate dose cohort may be opened at 6.0 mg mRNA-2416.

9 **SELECTION OF PATIENTS**

9.1 **INCLUSION CRITERIA**

All patients must meet all of the following inclusion criteria:

1. Males or females ≥ 18 years of age who have provided written informed consent prior to completing any study-specific procedure
2. Disease state and prior therapies:

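### Arm B Grade 2 events that become DLTs only by failing to resolve can still be open at Day 28, and the 3+3 rules do not hold the count for them

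*Protocol*

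**What the plan says.** Protocol 8.4.2 defines a DLT as a treatment-related event occurring in the first 28 days of therapy. For Arm B it adds a table by event type and grade. Four Grade 2 cells include a time-to-resolution test:

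- Myositis/polymyositis: "Events that do not resolve to Grade 1 within 30d OR exhibit signs of respiratory insufficiency regardless of optimal medical management".
- Peripheral neuromotor syndromes: the same 30-day limit, with respiratory insufficiency or autonomic instability as immediate triggers.
- Pneumonitis: "Non-infectious pneumonitis that does not resolve to Grade" 1 or lower within 10 days.
- Myocarditis: "Events that do not resolve to Grade 1 within 3d OR a biopsy confirms immune-mediated myocarditis".

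Protocol 8.4.4 runs the 3+3 on a fixed 28-day clock. A patient is evaluable after at least 28 days of follow-up, "or have experienced a DLT within 28 days of the first dose". On timing: "Dose escalation determination will not occur until the third patient in a cohort has completed their first 28-day study therapy". The first escalation rule begins: "If no patient (0 of 3) in a dose cohort experiences a DLT during the first 28 days, then the next dose cohort" is enrolled, subject to consensus of the Safety Review Committee (SRC).

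Protocol 8.4.3 sets the MTD boundary at fewer than 2 of 6 patients with a DLT in the first 28 days. It lets enrollment be held if two or more DLT-type events are observed after Day 28, and adds: "These events will not affect the determination of the MTD but will be used in determining the appropriate RDE". Protocol 8.4.1 says that the escalation guidelines in 8.4.4, with the stopping rules, "will be used as the basis for all SRC decisions". The Figure 1 note and SAP 9.1.1 also give a fixed 28-day window. No section defines a pending DLT.

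**The concern.** The DLT definition and the escalation clock do not fit together. A Grade 2 myositis that starts on Day 10 and is unresolved on Day 28 is neither a DLT nor cleared of being one. Section 8.4.4 has only two states at Day 28: the patient has had a DLT, or the patient has 28 days of follow-up and has not. The literal rule puts this patient in the second state.

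DLT incidence is a Phase I primary endpoint and determines the Arm B MTD. One misclassified patient is enough to change a decision. At 0/3 the dose is escalated, while at 1/3 three more patients are enrolled. At 1/6 the dose is within the MTD definition, while at 2/6 it exceeds it. If the criterion is then met on, say, Day 40, the late-event sentence in 8.4.3 can be read as keeping it out of the MTD.

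**Working it through.** **The plan's own boundary.** 1/6 = 16.7% is allowed and 2/6 = 33.3% is not. This agrees with the definition in 8.4.3 (fewer than 2 of 6, below 33%).

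**When each clause can be settled.** The inputs are the clause lengths in 8.4.2 and the Day 28 decision point in 8.4.4. The first dose is Day 1. Clause end = onset day + clause length, and the clause is open at Day 28 if its end falls after Day 28 and the event has not resolved.

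| Grade 2 clause | Earliest end (onset Day 1) | Onset days open at Day 28 | Latest end (onset Day 28) |
|---|---|---|---|
| Neuromotor, myositis (30 d) | 1 + 30 = Day 31 | all, Days 1–28 | 28 + 30 = Day 58 |
| Pneumonitis (10 d) | 1 + 10 = Day 11 | after 28 − 10 = 18: Days 19–28 | 28 + 10 = Day 38 |
| Myocarditis (3 d) | 1 + 3 = Day 4 | after 28 − 3 = 25: Days 26–28 | 28 + 3 = Day 31 |

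**Effect of the sentinel stagger.** Section 8.2.3 puts 7 days between the sentinel and the other patients in the 4 mg cohort, so the sentinel is at Day 28 + 7 = 35 or later at review. At Day 35, a 30-day clause is open for the sentinel only for onset after 35 − 30 = Day 5. A 10-day clause is open only for onset after 35 − 10 = Day 25. A 3-day clause is never open, because its latest end is Day 31. The other patients in that cohort do not gain this margin. The same section lets subsequent cohorts enroll up to three patients at a time, so at 8 mg all three may be near Day 28 at review.

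**Cases already settled.** These are events that resolve before Day 28, neuromotor or myositis events with respiratory insufficiency, neuromotor events with autonomic instability, and biopsy-confirmed myocarditis. Grade 3 cells with 14- or 30-day limits matter only if the table overrides the bullet below it, which makes almost any related event of Grade 3 or higher a DLT.

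**Illustrative size.** The documents give neither input below, so both are assumptions. Let *q* be the proportion of patients with a true DLT that is missed this way, and *p* the true DLT rate.

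- P(at least one missed in a cohort of 3) = 1 − (1 − q)³. For q = 1%, 3% and 5% this is 3.0%, 8.7% and 14.3%.
- P(3+3 clears the dose) = (1 − p)³ + 3p(1 − p)⁵. At p = 0.30 this is 0.343 + 0.151 = 49.4%. Missing a proportion q lowers the counted rate to p − q. At 0.29, 0.27 and 0.25 the dose clears with probability 51.5%, 55.7% and 60.0%.

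**The case against.** The strongest reply is that 8.4.2 already attributes by occurrence. An event that starts on Day 10 occurred inside the window whenever its criterion is met, and using 8.4.3 to exclude it is strained because it was not first observed after Day 28. That is the better reading of attribution. It does not settle timing: 8.4.4 still permits the decision at Day 28, before the criterion can be met.

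Second, Day 28 is a floor and not a deadline. Escalation needs SRC consensus, and the SRC reviews all available safety data and may add patients to the cohort. A careful committee could avoid the error, but nothing requires it to wait. The only written hold, in 8.4.3, needs two or more events, is optional, and leaves the MTD unchanged.

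Third, there are later safeguards. Dose Confirmation treats at least 3 more patients, and Section 8.2.7 tracks the DLT rate at the selected dose against 33% during expansion, possibly including escalation patients. Appendix E holds dosing for the affected patient. These limit the consequences. However, Dose Confirmation runs under the same 8.4 rules, the expansion check comes after escalation and takes its evaluability definition from 8.4.4, and Appendix E does not address the cohort count.

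Fourth, exposure is narrow. Arm B has one planned upward step (4 to 8 mg) with durvalumab fixed, and only four event types are involved, which may be rare at Grade 2. This stands, and it is why no firm effect size can be given. It is also fair that the Figure 1 note is only a schema label and that SAP 9.1.1 governs tabulation, not escalation. The SAP section lists only the Arm A-type Grade 3–5 criteria, which is a separate problem.

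**Conclusion.** The concern holds. For the two 30-day clauses the mismatch is certain from the text: no onset inside the window can be confirmed by non-resolution by a patient's own Day 28. For pneumonitis and myocarditis it is confined to the last 10 and last 3 days of the window. Followed literally, the rules can clear a dose while a protocol-defined DLT is pending.

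The size depends on how often such events occur and on what the SRC chooses to do, and the documents quantify neither. The rise from 49.4% to between 51.5% and 60.0% rests entirely on the assumed 30% true DLT rate and 1–5% missed proportion. The real effect may be smaller. The point should still be fixed, because it affects a Phase I primary endpoint and the dose taken into an Arm B expansion of up to about 45 patients, and the remedy is cheap.

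**What to change.** Keep the 3-, 10- and 30-day thresholds and change the timing rules:

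1. In 8.4.2, state that a DLT is attributed by onset within the first 28 days, even if the non-resolution criterion is met later.
2. In 8.4.4, define a patient with a qualifying event unresolved at Day 28 as DLT pending. That patient is not counted as DLT-free, and no escalation is made on that count until the event resolves or the clause ends (at the latest Day 31, 38 or 58 for the 3-, 10- and 30-day clauses).
3. In 8.4.3, limit the sentence on events beyond the first 28 days to events with onset after Day 28.

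This is protocol wording only, with no change to thresholds or sample size. The cost is a delay to the cohort decision of up to about 30 days for neuromotor or myositis events, 10 days for pneumonitis and 3 days for myocarditis, incurred only when such an event is open at Day 28.
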